	 Secondary endpoints include comparing differences among the two arms in the following: Incidence of worsening heart failure during hospitalization requiring IV inotropic therapy, new admission to an intensive care unit, new non-invasive positive pressure ventilation with bi-level positive airway pressure, or increase in the IV diuretic protocol intensity by 2 rows after Study Day 1 as adjudicated by the Clinical Event Committee Hospital readmission within 30 days of discharge for heart failure or diabetic reasons as adjudicated by the Clinical Event Committee
	 Exploratory endpoints include comparing difference among the two arms in the following: NT-proBNP at baseline to discharge adjusted for baseline Urine-output based Diuretic efficiency: 24-h total urine output (ml) per 40mg of IV furosemide equivalents on day 2 of IV diuretic therapy from 24-h urine collection (collected day 2-day 3) Fractional excretion of sodium (FENa)-based diuretic efficiency on day 2 of IV therapy: FENa per 40mg of IV furosemide equivalents of bolus loop dose using spot urine collected 2 hours after bolus loop dose Urinary Na/K ratio at day 2 of IV therapy adjusted for baseline Calculated 6-hour sodium output on day 2 of IV therapy using spot urine sodium collected 2 hours after bolus loop dose Length of hospital stay, measured as days from admission to discharge Presence of symptoms of congestion and dyspnea at discharge, measured via blinded-physician exam and patient reported congestion scores

	 Hospital readmission within 30 days of discharge for any cause Number of days at home without hospitalization or emergency room visit during 30-day follow up period Mean serum glucose during therapy Amount of total daily insulin doses (units) utilized per day during therapy among patients with diabetes, compared between treatment arms and to a prior to enrollment outpatient insulin regimen serum potassium covariate adjusted for baseline with attention to both elevation and depression

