	 Safety endpoints from study medication administration to hospital discharge: estimated Glomerular Filtration Rate by the MDRD equation at discharge adjusted for baseline Incidence of ketoacidosis Serum glucose covariate adjusted for baseline with attention to both elevation (> 400mg/dl) and depression (< 70mg/dl) Incidence of hypovolemic hypotension, defined as symptomatic hypotension with a sustained systolic blood pressure less than 90 mmHg over 30 minutes requiring fluid administration Inpatient mortality
Study Design	This is a randomized trial of the addition of dapagliflozin to patients with or without diabetes hospitalized with AHF. Participants will be recruited following an initial standard evaluation in the ED and randomized within 24 hours of presentation for AHF in a 1:1 fashion to protocolized diuretic therapy or dapagliflozin + protocolized diuretic therapy.
Number of Participants	240 participants will be randomized
Trial Location	Up to six sites including but not limited to:
	 Vanderbilt University Medical Center St Thomas Hospital System Centennial Hospital University of Mississippi Integris Baptist Medical Center

	University of North Carolina
Inclusion	1) Age of 18 years or older
Criteria	2) Randomized within 24 of presentation during a hospital admission for hypervolemic decompensated heart failure defined as either:
	 pulmonary artery catheterization with a pulmonary capillary wedge pressure greater than 19mmHg plus a systemic physical exam finding of hypervolemia (peripheral edema, ascites, or pulmonary edema on auscultation) in the absence of pulmonary artery catheterization data 2 of the following signs or symptoms: peripheral edema, ascites, jugular venous pressure > 10mmHg, orthopnea, paroxysmal nocturnal dyspnea, 5-pound weight gain, or signs of congestion on chest x-ray or lung ultrasound
	3) Planned or current use of IV loop diuretic therapy during current hospitalizaiton
	4) eGFR \geq 25 ml/min/1.73m ² by the MDRD equation

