- Amount of total daily insulin doses (units) utilized per day during therapy among patients with type 2 diabetes, compared between treatment arms and to a prior to enrollment outpatient insulin regimen
- serum potassium covariate adjusted for baseline with attention to both elevation and depression

Single-Center Exploratory Outcomes at Vanderbilt University Medical Center

The following exploratory outcomes will only be performed in patients at Vanderbilt University Medical Center who elect to participate in a sub-study. Patients can decline to participate in this sub-study and still participate in parent clinical trial. To explore changes in the plasma proteome during IV diuresis, we will collect one 15mL blood sample (10mL in purple top EDTA tube and 5mL in red top tube) at baseline and on the final study day (Day 5 or discharge).

2.4 Safety Outcomes: Compared between treatment arms during the index stay from signing of informed consent to hospital discharge

- Change in the estimated Glomerular Filtration Rate by the MDRD equation at discharge adjusted for baseline
- Incidence of ketoacidosis, identified by the study team as elevated ketones in the urine and an arterial blood pH < 7.35 and adjudicated by the Clincal Events Committee
- Serum glucose covariate adjusted for baseline with attention to both elevation (> 400mg/dl) and depression (< 70mg/dl)
- Potential prolonged hospitalization as a result of hypoglycemia requiring medical intervention as adjudicated by the Clinical Events Committee
- Potential prolongation of hospitalization as a result of incidence of hypovolemic hypotension, defined as a symptomatic hypotension with a sustained systolic blood pressure less than 90 mmHg over 30 minutes and requiring medical intervention as adjudicated by the Clinical Events Committee. All hypotension episodes requiring medical intervention will be evaluated by the Clinical Events Committee.
- Inpatient mortality

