 - a. Repeated as per doubling of the cumulative Day 2 loop diuretic dose (log2 cumulative loop diuretic dose centered at 40mg)
- d) Spot urine sodium-based diuretic efficiency defined as the spot urine sodium concentration (mmol/L) on Day 2 per 40mg of IV furosemide equivalents (preceding loop diuretic dose)
- e) Fractional excretion of sodium (FENa)-based diuretic efficiency on Day 2 of IV therapy defined as the FENa from a spot urine test on Day 2 of IV therapy collected ~2 hours after bolus loop dose per 40 mg of IV furosemide equivalents.
 - a. Repeat as per doubling of the cumulative loop diuretic dose (log2 cumulative loop diuretic dose centered at 40mg)
- f) Urinary Na/K ratio at Day 2 of IV therapy adjusted for baseline.
- g) Calculated 6-hour sodium output on Day 2 of IV therapy using spot urine sodium collected 2 hours after bolus loop dose.
- h) Length of hospital stay, measured as days from admission to discharge
- i) Presence of symptoms of congestion and dyspnea at discharge, measured via blinded-physician exam and patient reported congestion scores.
- j) Hospital readmission within 30 days of discharge for any cause.
- k) Number of days at home without hospitalization or emergency room visit during 30-day follow up period.
- 1) Mean serum glucose during therapy
- m) Amount of total daily insulin doses (units) utilized per day during therapy, compared between treatment arms and to a "prior to enrollment" outpatient insulin regimen.
- n) Analyze the change in basic metabolic panel laboratory values and hemoglobin from baseline to end of study
- o) Serum potassium covariate with attention to both elevation and depression.

Hypokalemia levels are defined as

- a. Not hypokalemic: serum potassium > 3.4 mEq/L
- b. Mild: serum potassium 3.0 3.4 mEq/L
- c. Mod-Severe: serum potassium < 3.0 mEq/L

Hyperkalemia levels are defined as

- a. Not hyperkalemic: serum potassium < 5.1 mEq/L
- b. Mild: serum potassium 5.1 5.5 mEq/L
- c. Severe: serum potassium > 5.5 mEq/L

Safety Endpoints: Comparing differences among the two arms in the following:

- a) Estimated Glomerular Filtration Rate by the MDRD equation at discharge adjusted for baseline. A sensitivity analysis of eGFR by the CKD-EPI equation will also be done.
- b) Incidence of ketoacidosis as adjudicated by the CEC
- c) Serum glucose with attention to both elevation and depression.
 - a. Hypoglycemia is defined as:
 - i. Not hypoglycemic: serum glucose > 70 mg/dl

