- b) A time to event analysis is proposed to assess the association of 30-day hospital readmission for ADHF or diabetes-related reasons. Cumulative incidence of hospital readmission for heart failure or diabetes-related reasons will be graphed by treatment arm death as a competing risk. Multivariable Cox proportional hazards models stratified by enrollment site will be fit to assess the association of time to hospital readmission for reasons of interest with treatment assignment.

Exploratory Analyses:

Appropriate model diagnostics will be run to assess model fit. If model diagnostics suggest the planned approach violates necessary assumptions, alternative methods will be pursued.

- a) The association of NT-proBNP at discharge with treatment arm will be modeled using covariateadjusted PO regression, adjusting for NT-proBNP at baseline (Day 1).
- b) The association of Day 2 24-hour total urine output per the following methods in which diuretic dose is centered at 40mg and values less than 40mg are winsorized to 40mg:
 - a. 40 mg of IV furosemide equivalents will be analyzed using the Wilcoxon Rank Sum test
 - b. Doubling of the loop diuretic dose to account for the logarithmic dose-response curve will be analyzed using the Wilcoxon Rank Sum test.
- c) Urine sodium-based diuretic efficiency defined as the Day 2 24-hour total urine sodium excretion (mmol) per 40mg of IV furosemide equivalents (total loop diuretic dose over Day 2) will be analyzed using the Wilcoxon Rank Sum test.
 - a. Repeated as per doubling of the cumulative Day 2 loop diuretic dose (log2 cumulative loop diuretic dose centered at 40mg) will be analyzed using the Wilcoxon Rank Sum test.
- d) Spot urine sodium-based diuretic efficiency defined as the spot urine sodium concentration (mmol/L) on Day 2 per 40mg of IV furosemide equivalents (preceding loop diuretic dose) will be analyzed using the Wilcoxon Rank Sum test.
- e) The association of Day 2 fractional excretion of sodium (FENa)-based diuretic efficiency determined from spot urine collected 2 hours after bolus loop dose with treatment arm will be analyzed using the Wilcoxon Rank Sum test.
- f) The association of Day 2 urinary Na/K ratio with treatment arm will be analyzed using covariateadjusted PO regression, adjusting for baseline (Day 1) urinary Na/K ratio.
- g) The association of calculated Day 2 6-hour sodium output with treatment assignment will be analyzed using the Wilcoxon Rank Sum test

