All multivariable models will adjust for the same key covariates as specified for the primary outcome, as sample size permits. Appropriate model diagnostics will be run to assess model fit. If model diagnostics suggest the planned approach violates necessary assumptions, alternative methods will be pursued.

- a) The association of estimated Glomerular Filtration Rate (eGFR) at discharge, calculated using the MDRD equation, with treatment assignment will be modeled using covariate-adjusted PO regression, adjusting for baseline eGFR. The analysis will be repeated calculating eGFR using the CKD-EPI equation as well.
- b) The association of the incidence of ketoacidosis as adjudicated by the CEC with treatment assignment will be analyzed using the Pearson chi-square test.
- c) Serum glucose trends over time by treatment assignment will be graphed. Descriptive statistics of the daily raw glucose values and the glycemic status during hospitalization by treatment group will be reported and compared across treatment assignment by Wilcoxon Rank Sum tests and Pearson's chi-square tests, respectively.
- d) The association of incidence of hypovolemic hypotension, defined previously, with treatment assignment will be analyzed using the Pearson chi-square test.

e) The association of inpatient mortality with treatment assignment will be analyzed using the Pearson chi-square test and univariate logistic regression.

Sensitivity Analyses:

Our sensitivity analysis will be a covariate-adjusted proportional odds (PO) regression model with our outcome being log-transformed weight at the minimum of Day 5 or discharge and the main predictor being treatment assignment. Adjusting covariates will be as defined in the primary analysis. Appropriate model diagnostics will be run to assess model fit. If model diagnostics suggest the planned approach violates necessary assumptions, alternative methods will be pursued.

Heterogenicity of Treatment Effect:

Heterogenicity of Treatment Effect (HTE) will be assessed refitting the primary model with the covariate of interest interacted with treatment assignment. The HTE analysis will include the following variables:

- Sex (male or female)
- Baseline edema score (No-Mild/Moderate/Severe)
- Baseline NTproBNP
 - Continuous
 - Dichotomize by median NTproBNP [above/below]
- Baseline BMI-adjusted BNP: defined as a 4% increase in NT-proBNP for every 1 unit increase in baseline BMI above a BMI of 20kg/m²
 - Continuous

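### The SAP drops the protocol's baseline adjustment for serum glucose (safety) and serum potassium (exploratory), while keeping it for the other three laboratory endpoints

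*SAP*

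**What the plan says.** **Protocol.** Five laboratory endpoints carry adjustment for baseline in their definition. Two are in the safety list (section 2.4 and the Clinical Trial Summary): "Serum glucose covariate adjusted for baseline with attention to both elevation (> 400mg/dl) and depression (< 70mg/dl" and "estimated Glomerular Filtration Rate by the MDRD equation at discharge adjusted for baseline". Three are in the exploratory list (section 2.3 and the Summary): "serum potassium covariate adjusted for baseline with attention to both elevation and depression", "Urinary Na/K ratio at day 2 of IV therapy adjusted for baseline", and NT-proBNP at discharge. Section 10.0 states the principle: the baseline value enters as a covariate, and change from baseline is not analysed, so that the baseline relation need not be linear with slope 1. For safety labs it promises the most powerful continuous analyses, together with the empirical distribution function. It leaves the full methods to the SAP.

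**SAP.** Three of the five keep a PO model with the lab's own baseline: NT-proBNP (Exploratory Analyses a), "adjusting for NT-proBNP at baseline (Day 1"), urinary Na/K (Exploratory Analyses f)) and eGFR (Safety Analyses a)). For the other two the endpoint wording has lost the adjustment. Safety Endpoints c) reads "Serum glucose with attention to both elevation and depression". Exploratory Endpoints o) reads "Serum potassium covariate with attention to both elevation and depression", where the word covariate has been left without its object. The analyses match: Safety Analyses c) says "Descriptive statistics of the daily raw glucose values and the glycemic status during hospitalization by treatment group will be reported and compared", with Wilcoxon tests for the values and chi-square tests for status, and Exploratory Analyses o) does the same for potassium. Neither item says whether a test uses one day, one value per patient or something else, or how status during hospitalization is assigned to a patient.

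**The concern.** The SAP departs from the protocol's definition of a named safety endpoint and of one exploratory endpoint, and gives no reason. The change log reports new potassium and glucose categories, and analysis changes that follow from the glucose categories. It does not report that the baseline adjustment was removed. The potassium fragment suggests an editing slip, though the documents do not settle that.

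What is at stake is precision on glucose and potassium. Protocol section 2.1 says that, even if the primary endpoint is missed, the study should still establish safety, and it names glycemic outcomes among those examined. A less precise glucose comparison makes a real shift easier to miss. A second, smaller matter is that two analysts could follow the same SAP text and report different p-values, because the unit of analysis is not stated.

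**Working it through.** **1. Endpoint by endpoint.**

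| Lab endpoint | Protocol | SAP analysis | Own baseline in the model? |
|---|---|---|---|
| NT-proBNP (exploratory) | adjusted | PO model, Exploratory a) | yes |
| Urinary Na/K (exploratory) | adjusted | PO model, Exploratory f) | yes |
| eGFR (safety) | adjusted | PO model, Safety a) | yes |
| Potassium (exploratory) | adjusted | Wilcoxon, chi-square, Exploratory o) | no |
| Glucose (safety) | adjusted | Wilcoxon, chi-square, Safety c) | no |

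The count is five in the protocol, three kept and two dropped.

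**2. Does other SAP text restore it?** The opening sentence of Safety Analyses concerns multivariable models and the primary covariates, which now means baseline weight. Wilcoxon and chi-square tests are not multivariable models, and weight is not the lab's baseline. Exploratory n) compares change from baseline to end of study in the basic metabolic panel, which would normally include both labs. That is an unadjusted change score. Exploratory l) tests mean glucose during therapy without baseline.

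**3. The plan's own power figure.** The documents give no power figure for these labs. The only one is 87% for the primary endpoint, and it reproduces: P = Φ(0.1/(0.25·√2)) = 0.611, and power = Φ(0.4·√60 − 1.96) = Φ(1.138) = 87.3% by the normal formula. It is not in question here.

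**4. Size of the loss.** From the documents: 120 per arm and two-sided 0.05. Assumed, because the documents give neither: correlation r between baseline and follow-up of 0.3, 0.5 or 0.7, and a true shift of 0.35 SD. Normal data with equal SD at both times are also assumed.

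Power ≈ Φ(0.35·√60·√(3/π)/s − 1.96), where 0.35·√60 = 2.711, √(3/π) = 0.977 and the product is 2.649. The residual SD is s = 1 for raw values, √(2(1−r)) for change and √(1−r²) for baseline adjustment.

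| r | Raw Wilcoxon | Change score, as in n) | Baseline-adjusted |
|---|---|---|---|
| 0.3 | Φ(0.689) = 75% | s = 1.183, Φ(0.279) = 61% | s = 0.954, Φ(0.817) = 79% |
| 0.5 | 75% | s = 1.000, Φ(0.689) = 75% | s = 0.866, Φ(1.099) = 86% |
| 0.7 | 75% | s = 0.775, Φ(1.460) = 93% | s = 0.714, Φ(1.750) = 96% |

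Simulation gave about 75% for raw Wilcoxon at each r, 62/76/92% for Wilcoxon on change, and 78/85/95% for the PO model (fitted on deciles of the outcome). A repeat run for change gave 59/75/93%, so read these to within about three points. Null rejection of the adjusted PO model was 5.3 to 5.5%, and of raw Wilcoxon 4.8 to 5.2%.

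In sample-size terms, an unadjusted test needs 240/(1−r²) = 264, 320 or 471 patients to match 240 with adjustment.

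**5. Day-by-day testing.** Appendix A marks chemistries on Days 2 to 5, and section 5.0 asks for at least one panel daily, so 4 to 5 values per patient. If each day is tested separately, every test holds 5%. The simulated chance of at least one p < 0.05 per lab is 13 to 18% over 4 days and 15 to 21% over 5, across the three correlations. Under independence it would be 1 − 0.95⁴ = 18.5% and 1 − 0.95⁵ = 22.6%.

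**The case against.** The protocol leaves full methods to the SAP, so the SAP may choose the test. The log does announce analysis changes tied to the new glucose categories. Glucose already has a per-patient continuous test in l), and n) brings in baseline for the metabolic panel. At r = 0.7 the change score reaches about 92% against 95% for the adjusted model, and at r = 0.3 adjustment lifts the raw test only from 75% to 78%. Glucose in patients with diabetes is titrated by algorithm, so a high correlation cannot be presumed. No alpha control is claimed for these endpoints.

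Most of this stands and limits the size of the point. It does not remove it. Item n) is the method that section 10.0 says the trial avoids, and below r = 0.5 it has less power than ignoring baseline. Covariate adjustment is at least as good at each correlation considered, and the true r need not be known in advance.

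A reader might infer four stronger things that the documents do not support:

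- **That the tests are invalid because patient-days are pooled.** The SAP does not say so. Separate tests by day are the more natural reading of daily values, and with one value per patient the tests hold their level.
- **That baseline is ignored altogether.** Item n) uses it, in a weaker form.
- **That the SAP withdraws the empirical distribution function.** It only fails to repeat it, and section 10.0 still promises it.
- **That the adjustment was removed on purpose.** Nothing in the documents shows intent.

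**Conclusion.** The mismatch is real. Two of five baseline-adjusted laboratory endpoints, one of them a safety endpoint, are analysed without the adjustment that defines them, and no explanation is given. The consequence is lost precision, with no bias and no loss of validity when there is one value per patient. Against the better of the raw and change-score tests already planned, the adjusted PO model gains about 3 points of power at r = 0.3 (75% to 78%), 9 at r = 0.5 (76% to 85%) and 3 at r = 0.7 (92% to 95%). Against the raw test alone, which is what items c) and o) specify, the gains are 3, 10 and 20 points. These figures rest on an assumed correlation and an assumed 0.35 SD shift.

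The day-by-day error of 13 to 21% is secondary. Primary and secondary endpoints are unaffected. The change is worth making because it restores agreement with the protocol at almost no cost.

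**What to change.** In Safety Analyses c) and Exploratory Analyses o), make the main continuous comparison a PO regression with treatment and the baseline value of that lab, as already planned for eGFR. Choose one of two forms and state it:

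- **Per-patient values that cover both directions**, for example the lowest and highest post-randomisation value plus the last value, over a stated window. A single last value would miss transient lows and highs.
- **One PO model of all daily values**, with treatment, day and baseline, and cluster-robust errors by patient. In simulation its null rejection was 5.0 to 5.7%. This replaces a separate test for each day.

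Restore the words on baseline adjustment in Safety Endpoints c) and Exploratory Endpoints o). The planned chi-square tests of glycemic and kalemic status may stay, with status defined once per patient. Show the days observed by arm, because lowest, highest and worst values depend on length of stay.

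Minor points to settle in the same edit:

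- Show the empirical distribution function by arm, as section 10.0 promises.
- Assign exactly 70 mg/dl to a glucose class. It now falls between the classes above 70 and 54 to 69, while the protocol's cut is below 70.
- Reconcile the protocol's elevation threshold of above 400 mg/dl with the SAP's severe class of above 300 mg/dl.

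The cost is a few sentences in the SAP and slightly more programming. Baseline and daily chemistries are already collected (Clinical Trial Summary, section 5.0, Appendix A).
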